## 9.6: Data Analyses

### 9.6.1 Exploratory analyses of outcomes and mediators.

Exploratory analyses will involve first examining variable distributions and missing data patterns. Next, we will conduct exploratory analyses to assess patterns of change associated with participation in the programs. The study is not expected to produce a quantity of data large enough to have adequate power to detect significant effects of the MFY program compared to the TFY control program. However, trends in incident depression (primary outcome, PROMIS Pediatric Depression Scale), change in depression scores (combined SMFQ-C, PROMIS Pediatric Depression Score) resilience (secondary outcome), and potential mediators will be examined by program arm.

To assess incident depression, we will use exploratory nonparametric (Kaplan-Meier plots) to examine the trends in incident depression within and between treatment arms using the PROMIS Pediatric Depression Scale short-form..

To address the change in depressive symptoms (secondary outcome), we will examine the paired t-test in each condition, to test for any effect of either program. Subsequently, an exploratory analysis will examine the trajectory of changes over time by program arm, using graphical representations of outcomes at each time point by subject, cohort, and program arm as well as longitudinal random effects models. Hence, a within-group model would include terms for the follow-up depression score, the overall intercept, the cohort effect, the time effect, and a cohort\*time interaction—to allow the trajectory to vary by cohort—as well as random effects for individual subjects and subjects nested within cohorts.

Additional explorations will include bivariable associations (correlation, simple regressions) between the process measures and the outcome, between intervention assignment and process measures, between intervention assignment and potential mediators, and between process measures and outcomes. If indicated, mediation analyses will be conducted to investigate possible mechanisms; strength of mediation (indirect effect) will be calculated as the product of the association of the causal variable on the mediator and the association of the mediator on the outcome variable.

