### Design and Outcomes

Four cohorts of adolescents, each with 20 participants, will be recruited. In each cohort, twenty individuals will be randomized with 10 each in the mindful self-compassion group (Making Friends with Yourself) and the healthy behavior skills group. In addition, each adolescent will be accompanied by a parent (n=80). Adolescents complete brief weekly questionnaires to assess depressive symptoms as well as a longer set of online questionnaires at baseline, weeks 4 and 8 of the intervention, and 3 and 36 weeks post-intervention. Parents complete a questionnaire at baseline, 3 and 36 weeks post-intervention.

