**Short Mood and Feelings Questionnaire (SMFQ)**: The SMFQ is a depression scale created for children and adolescents. There is a 13-item youth version (**SMFQ-C**) and 13-item parent version (**SMFQ-P**). Items are symptoms of depression experienced over the past 2 weeks which the child or parent would endorse as “not true”, “sometimes true” or “true”. Internal reliability has been reported as  $\alpha=.85$  (SMFQ-C) and  $\alpha=.87$  (SMFQ-P).

**Brief Resiliency Scale (BRS)**: This scale defines resiliency as the ability to “bounce back” and recover from stress; the items reflect a sense of personal agency. Six items are rated on a scale from 1 (*strongly disagree*) to 5 (*strongly agree*). Convergent and discriminant validity have been established, and Cronbach’s alpha is between .80 and .91. Test-retest reliability over one month has been reported as .69 and >22 weeks as .62.

**Adolescent Cognitive Style Questionnaire (ACSQ)**: The ACSQ assesses the extent to which adolescents utilize a negative cognitive style. Twelve hypothetical negative event scenarios are presented that are relevant to teens, and the participant is asked to write down one potential cause for the event. Participants then rate the degree to which the cause is 1) internal, 2) stable, and 3) global, the likelihood for future negative consequences to occur as a result, and the degree to which the result implies that the self is flawed. Construct validity was supported through correlations with other attributional style measures and depressive symptoms, and the scale demonstrated internal consistency ( $\alpha=.95$ ) and test-retest reliability (.73 over 2 weeks). Reliability and validity remain consistent with using as few as four scenarios. This study uses six of the twelve scenarios (items 1, 2, 3, 6, 8, and 12) that are relevant to the study population. Items not as relevant (e.g. attending college, having a boss) or that were redundant (e.g. questions dealing with boyfriends/girlfriends or grades) were not included for this study to reduce participant burden with answering questions.

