### 9.1: General Design Issues

This study is a planning grant for development of an adequately powered clinical trial. Statistical hypotheses are not considered relevant to this mechanism. Randomization is designed to assess feasibility of our randomization plan, in addition to general feasibility issues of the delivery of the educational programs.

In our third aim, we proposed exploratory analysis of clinical outcomes (see below).

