## 9.2: Sample Size and Randomization

### 9.2.1: Treatment Assignment Procedures

Participants are randomized to treatment assignments to test the acceptability of randomization in the population. Random allocation, stratified by gender, is assured by a computer-generated assignment accessible to the REDCap administrator, but group assignment cannot be masked, except to quantitative data analysts.

**Power and sample size.** Untreated, >30% of adolescents are expected to develop incident depression. Power is calculated for time to incident MDD. With a sample size of 80, we expect to have 80% power to detect a hazard ratio of 0.52 for time to MDD between the groups. It is anticipated that we will screen 160 with the QIDS and 120 with the DISC to achieve a sample of 80 eligible teens (with 80 parents). Our target recruitment estimate is 53 females and 27 males, based on research demonstrating that there are twice as many female teens with subsyndromal depression as males. **Note that all enrollment figures refer to teens.** Each will have the involvement of one parent.

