### 9.5.2: Secondary Outcomes

For the secondary outcome, assuming feasibility is established, change in the Short Mood and Feelings Questionnaire (child and parent versions) will be examined in a linear regression in each condition, to test for any effect of either program. Then we will examine the change in depression scores through an

ANCOVA model controlling for baseline depression score and cohort to control for group specific effects. Subsequently, an exploratory analysis will examine the trajectory of changes over time by program arm, using graphical representations of outcomes at each time point by subject, cohort, and program arm as well as a longitudinal random effects model.

Hence, a within-group model would include terms for the follow-up depression score, the overall intercept, the cohort effect, the time effect, and a cohort\*time interaction—to allow the trajectory to vary by cohort—as well as random effects for individual subjects and subjects nested within cohorts. Between program arms, we would add terms for the program arm and its interaction with time.

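### Section 9.6.1 gives the mediators, self-compassion, mindfulness and resilience no baseline-adjusted arm comparison, although Visit 2 scores exist and 9.5.2 already has the model

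*Combined protocol and SAP*

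**What the plan says.** Section 9.6.1 describes the arm comparisons for these scales in one sentence. It begins "Additional explorations will include bivariable associations (correlation, simple regressions" and the pairs it then lists include "between intervention assignment and process measures, between intervention assignment and potential mediators". The sentence does not say whether the response is the follow-up score or the change from baseline, and it names no covariate. Resilience is mentioned in the same section only as something whose trend is examined by arm.

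Section 9.5.2 treats the depression score (SMFQ) differently. It specifies an "ANCOVA model controlling for baseline depression score and cohort to control for group specific effects", followed by a longitudinal random effects model. Both are written for the depression score; neither is extended to the other scales.

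Table 2 in 5.1.3 schedules BRS, ACSQ, RRS-B, TOSCA-A, SCS and CAMM at Visits 2, 6, 10, 13 and 16, so each has a baseline. The other process measures taken from participants (home practice, the credibility scale and the Feelings About the Class questionnaire) are collected only after classes begin. The weekly PROMIS form, also listed there, is the depression measure and not part of this point.

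**The concern.** According to Specific Aim 3 (section 1.2), these analyses are meant to inform the planning of an adequately powered trial. The arm effect on each mediator shows whether the program moves its proposed targets, and 9.6.1 uses the same quantity as the first factor in the mediation product. If it is estimated from follow-up scores alone, chance imbalance at baseline stays in the estimate and the interval is wider than the collected data require. The noise then carries into any indirect effect.

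The plan also treats similar scales unequally. The depression score has baseline and cohort in its model. The mediators, SCS and CAMM have neither, and the BRS has no stated model. The interventions may be modified between cohorts (second section numbered 5.1.3), so losing the cohort term matters as well as losing the baseline.

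**Working it through.** **Inputs**

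- Sample size 80, from 9.2.1: "With a sample size of 80, we expect to have 80% power to detect a hazard ratio of 0.52". Only the 80 is used here, not the hazard-ratio claim.
- Equal allocation, from the Précis: "twenty individuals will be randomized with 10 each in the mindful self-compassion group" and the same number in the control group, over four cohorts. Hence n = 40 per arm.
- Significance level not stated; two-sided 5% assumed.
- BRS correlations, from 5.1.3: "Test-retest reliability over one month has been reported as .69 and >22 weeks as .62".
- ACSQ correlation, from 5.1.3: "test-retest reliability (.73 over 2 weeks".
- RRS-B, TOSCA-A, SCS and CAMM: no over-time correlation is given, so ρ = 0.3 and 0.5 are added as assumed values.
- Standardised arm difference d: none is planned for these scales. I assume d = 0.5. Section 2.2 cites that value from a meta-analysis of mindfulness interventions with youth, for psychological symptoms in clinical samples.

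**The plan's own continuous-scale figure.** Section 7.2 of the Data Safety Monitoring Plan (Appendix IV) claims more than 80% power for a difference of 4 with SD 6 on the combined SMFQ. Using power = Φ(d√(n/2) − 1.96): (4/6) × √20 = 2.981, and Φ(1.021) = 84.6% (83.8% by noncentral t). The claim reproduces, so the method matches the plan's.

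**Residual variance, in units of the follow-up variance**

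- Follow-up score on arm only: 1
- Change score on arm only: 2(1 − ρ)
- ANCOVA on baseline: 1 − ρ²

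**Power = Φ(d√(n/2)/√v − 1.96)**, where v is the relevant variance. With d = 0.5 and n = 40, d√(n/2) = 2.236.

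- Unadjusted follow-up: Φ(0.276) = 60.9% (noncentral t 59.8%).
- ANCOVA at ρ = 0.62: v = 1 − 0.3844 = 0.6156, √v = 0.785, 2.236/0.785 − 1.96 = 0.89, Φ = 81.3%.
- Change score at ρ = 0.62: v = 0.76, √v = 0.872, 2.236/0.872 − 1.96 = 0.60, Φ = 72.7%.

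| ρ | Source | Variance cut, ρ² | ANCOVA power (noncentral t) | Change-score power | ANCOVA gain over follow-up score | ANCOVA gain over change score |
|---|---|---|---|---|---|---|
| 0.62 | BRS, over 22 weeks | 38% | 81.3% (80.4%) | 72.7% | 20.4 | 8.6 |
| 0.69 | BRS, one month | 48% | 87.1% (86.2%) | 81.1% | 26.2 | 6.0 |
| 0.73 | ACSQ, two weeks | 53% | 90.5% (89.8%) | 86.1% | 29.6 | 4.5 |
| 0.50 | assumed | 25% | 73.3% (72.2%) | 60.9% | 12.4 | 12.4 |
| 0.30 | assumed | 9% | 65.0% (63.9%) | 47.2% | 4.1 | 17.7 |

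Gains are in percentage points, from unrounded normal-approximation values.

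**Sensitivity to d.** At ρ = 0.62 to 0.73 and 40 per arm, the gain over an unadjusted follow-up comparison is 6 to 11 points at d = 0.2, 13 to 23 at d = 0.3, 18 to 30 at d = 0.37, and 12 to 15 at d = 0.667 (the SMFQ effect above). With 32 per arm, the 80% completion mark in 9.6.2, and d = 0.5 it is 21 to 32 points.

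**A reading that needs no d or significance level.** The 80 teens carry the information of 80/(1 − ρ²) unadjusted teens: about 130 at ρ = 0.62, 153 at 0.69 and 171 at 0.73.

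None of these figures allows for clustering by class or for any variance explained by cohort.

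**The case against.** The strongest reply is that the plan does not claim these analyses are powered. Section 9.1 says "Statistical hypotheses are not considered relevant to this mechanism", and 9.6.1 calls the comparisons explorations and says adequate power is not expected. Among randomised participants an unadjusted arm contrast is unbiased; what is lost is precision. That stands, and it is why power serves here only as an illustration. It does not justify giving up precision that the collected data would supply, in estimates intended for planning.

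A second reply is that the response is not named. Section 9.6.1 speaks of patterns of change, and a simple regression of change on arm is still bivariable yet uses the baseline. This also stands. It shrinks the gain at ρ = 0.62 to 0.73 to about 4 to 9 points. Change scores are not a safe default, however: below ρ = 0.5 they are noisier than unadjusted follow-up scores, and four of the six scales have no documented correlation.

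A reader might infer that the plan discards every baseline and gives up 20 to 30 points of power on all mediators and process measures. The documents do not support that:

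- The figure needs d near 0.5, ρ of 0.62 to 0.73 and follow-up scores as the response.
- Two of the three correlations belong to the BRS, whose model is unspecified rather than specified as unadjusted.
- The third is a two-week ACSQ value. That is shorter than any follow-up interval in this trial, which also uses six of the twelve scenarios (though 5.1.3 says as few as four suffice).
- Of the process measures at issue, only SCS and CAMM have a Visit 2 score.

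Nor does it follow that a real shift in a mediator would probably be missed: unadjusted power in the illustration is 60%.

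**Conclusion.** The point holds as a gap in specification with a near-free remedy. Section 9.6.1 names no baseline- or cohort-adjusted arm comparison for ACSQ, RRS-B, TOSCA-A, SCS or CAMM, leaves their response variable open, and names no model for BRS. All six have baselines, and the suitable model is already in the plan.

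The firmest measure of size is the variance reduction relative to an unadjusted follow-up comparison: 38% to 48% for BRS and 53% for ACSQ, if the quoted test-retest values carry over to this sample and these intervals. For the other four scales the size is unknown. The power figures (60% rising to 80–90% at those correlations, 72% at ρ = 0.5 and 64% at ρ = 0.3) rest on the assumed d = 0.5, 40 per arm, two-sided 5% and no clustering. The loss is one of precision in exploratory estimates; it does not touch the primary time-to-event analysis.

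**What to change.** In 9.6.1, state that follow-up BRS, ACSQ, RRS-B, TOSCA-A, SCS and CAMM are each analysed by the ANCOVA of 9.5.2: follow-up score on arm, that scale's own Visit 2 score, and cohort. Use the adjusted arm estimate as the first leg of any mediation product. Leave home practice, the credibility scale and the Feelings About the Class questionnaire as they are, since they have no baseline.

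The change is to wording only and needs no new data. Each model spends about four more degrees of freedom: one for baseline and three for four cohorts. Under the complete-case rule in 9.5, a teen without the Visit 2 score on a scale drops out of that scale's model, so the number analysed should be reported for each.

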### 9.6.2: Feasibility Analyses

Feasibility will be measured by the following:

1. Acceptance of the treatment and control programs as measured by attendance in 6 of 8 active intervention sessions and 4 of 6 continuation sessions;
2. Equivalence of the credibility of the two programs as measured with the credibility questionnaire;

3. Identification of recruitment challenges and their remedies as measured by:
  - a. the number of individuals screened;
  - b. the proportion of screened adolescents who qualify;
  - c. the number of qualifiers who enroll; and d) the number of enrollees who complete the program—80% completion defined by the acceptance criteria above defines a feasible program;
4. Identification of factors associated with subjects' willingness to adhere to the study protocol such as:
  - a. Location or timing of program classes, or lack of transportation;
  - b. Those not completing the program will be contacted for a telephone interview to evaluate factors leading to dropout.
5. Identification of study components fostering engagement in the study groups and materials.

### Subject Engagement

In addition to attendance data, engagement will be measured by:

1. Subjective class participation as rated by the instructor;
2. Adherence to recommended homework practice as measured in the daily diary;
3. Barriers for practice as captured in the diary;
4. Participant comments about the degree to which these practices have enabled them to adopt an attitude of mindfulness and self-compassion (as captured in the audio-taped class sessions). At the end of participation in the study, at month 8-9, subjects will be invited to give their impressions about the study in a brief, post-participation focus group or interview (see [Section 5.1.3, Qualitative Measures](#)).

### Program Fidelity

All program sessions will be audio-recorded. The purpose of the recording is two-fold:

1. To identify any systematic variations in instructors' attitude, communication, or behavior between treatment groups; to assess adherence to the protocol; and to screen for any group-dependent differences in communication in content or style between the instructors and subjects;
2. To capture participants' input and comments during the classes (see qualitative analysis).

An evaluation matrix will be developed based on the program manuals and other written protocols. Two members of the study staff will listen to selected program sessions independently to rate adherence to the protocol.

### Program Credibility

Credibility is measured by both the Borkovec and Nau questionnaire and qualitative data.

Acceptance of randomization is measured by a comparison of drop-out rates by intervention arm.

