### Objectives

The primary objective of this research project is to refine, manualize, and test the feasibility of the a mindfulness-based self-compassion program and an attention control program focused on developing healthy behaviors known to reduce depressive symptoms (e.g., exercise, healthy food choices, sleep hygiene, relationship skills) for 14-17 year-old adolescents with subsyndromal depression. Refinement of procedure manuals for adolescent participants and instructors will ensure that future interventions are delivered in a consistent and reproducible fashion.

A secondary objective is to test the feasibility of randomizing participants to the two educational programs. Results will guide the development of an adequately powered clinical trial in terms of recruitment needs and logistics; subjects' acceptance of the treatment and control programs; equivalence of the credibility of the two programs; and subjects' willingness to complete assessment instruments, adhere to study protocols, and complete the study.

Another secondary objective is to explore primary and secondary outcomes and mediators in response to the mindfulness-based program, including incident depression (primary outcome), change in depressive symptoms and resilience (secondary outcomes) and rumination, negative cognitive style, and shame (potential mediators).

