## 4. Selection and Enrollment of Participants

### 4.1: Inclusion Criteria

Participants must meet all of the inclusion criteria to participate in this study. Inclusion criteria for the study includes:

- Adolescents between ages 14-17. Adolescents may turn 18 after enrollment.

- Adolescents who are in high school.
- Adolescents with access to a smartphone or internet-enabled device.
- Adolescents and parent willing for their adolescent to be randomized to one of the two groups.
- Adolescent able to attend group sessions (8 weekly, 1.75 hour sessions; 6 monthly, 1.5 hour sessions) and complete study assessments.
- Adolescents experiencing subsyndromal depression assessed by:
  - Completion of screening questions by parent (see [Parent Screening Survey](#) and Telephone Consent);
  - Completion of QIDS by adolescent (see ;
  - Completion of clinical mental health assessment based on Diagnostic Interview Schedule for Children for Children (DISC-IV) by a study provider. The clinical mental health

assessment will screen for serious psychiatric illness, including major depression (MDD), suicidality, and other exclusion criteria.

Preliminary identification of subsyndromal depression will occur through screening questions completed by the parent (see Telephone Consent for details) and completion of QIDS by adolescent.

Adolescent and parent willing to receive a clinical mental health assessment, administered by a study provider, based on the Diagnostic Interview Schedule for Children-IV (DISC-IV) to screen for serious psychiatric illness, including major depression (MDD) and suicidality.

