#### 4.3.3: Documentation

The study team will maintain a screening log on REDCap (a secure, web-based research database) throughout the study. This will include names, dates of contact, and outcomes of the recruiting effort for each candidate. At all stages of the recruitment process, the study team will store any written documentation securely in locked study cabinets.

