#### 4.3.4: Randomization

Although the study is not designed as an RCT, we do plan to test our randomization system. In all but the first two cohorts, as soon as 14-20 eligible adolescents qualify for enrollment, they will be allocated to one of the educational groups, using a specially-designed computer program (in REDCap). This program requires the operator to check off inclusion/exclusion criterion for each subject and confirm that subjects have been consented. The program utilizes a random-numbers generator with a permuted block design (blocks of 2 to 4) to ensure that the numbers of subjects allocated to the two arms over time are equal and to conceal the allocation. Randomization is stratified by gender.

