### 6.2.3: Follow-up Visits

Following the eight-week program, participants will have self-report assessments 22 weeks after the program (Visit 13) and 36 weeks after the program (Visit 16, final evaluation).

## Visit 1

[Section 6.2.2](#), *Enrollment and Baseline Assessments*, provides a description of Visit 1.

## Visit 2

Study staff will send the study questionnaires via a link to parents and adolescents one week before the start of classes. Parents and adolescents will complete the online measures. Once measures are completed, study staff will notify the participants of their group assignment and logistics of participation (time, place, etc.)

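### Acceptability of randomisation is measured only by comparing drop-out between arms, which leaves out families who refuse randomisation and does not respond to loss shared by both arms

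*Combined protocol and SAP*

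**What the plan says.** The purpose is stated in section 9.2.1: "Participants are randomized to treatment assignments to test the acceptability of randomization in the population". The précis has a related but broader aim: "A secondary objective is to test the feasibility of randomizing participants to the two educational programs".

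The measure is one sentence under Program Credibility in section 9.6.2: "Acceptance of randomization is measured by a comparison of drop-out rates by intervention arm". It carries no threshold, test or margin.

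Four other passages bear on it:

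- Section 4.1 requires "Adolescents and parent willing for their adolescent to be randomized to one of the two groups".
- Under section 6.2.3 (Visit 2), once the baseline questionnaires are done, "study staff will notify the participants of their group assignment". This comes after consent and before the first class.
- Section 9.5 limits all statistical analyses to randomised adolescents who came to at least one class, although section 9.3 defines the intention-to-treat population as everyone randomised.
- Section 4.3.3 describes the screening log: "This will include names, dates of contact, and outcomes of the recruiting effort for each candidate". It does not ask for a reason when a family declines.

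**The concern.** A planning study should tell the next trial's designers how many families will not accept allocation by chance, and how many will leave once they learn the result. The first group never enters an arm here. The second enters the measure only as a difference between arms, and perhaps not at all if the rule in section 9.5 is applied. A small difference in drop-out could therefore be read as acceptance of randomisation when it says little about it, and the recruitment plan for the larger trial would lack a figure it needs.

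**Working it through.** The documents give no expected drop-out, refusal rate, threshold or significance level for this comparison, so there is no figure of the plan's to reproduce. The drop-out rates below and the two-sided 5% level are assumptions.

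**1. Refusal.** Families unwilling to be randomised fail section 4.1 and are never allocated. Whether 0% or 75% of those approached refuse, both arms' drop-out rates are unchanged. The nearest uptake metric, qualifiers who enrol (section 9.6.2 item 3c; 75% criterion in section 8 of the Data Safety Monitoring Plan), is not assigned to this purpose. Because willingness is itself an eligibility criterion, refusers can be counted as non-qualifiers and so leave its denominator.

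**2. Loss common to both arms.** If 10 of 40 leave each arm, the difference is 10/40 − 10/40 = 0. If drop-out is equal at 20%, 40% or 60%, Fisher's test rejects with probability 0.028, 0.030 and 0.030 at 40 per arm (0.023 to 0.024 at 20 per arm). The contrast does not move with the level of loss.

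**3. Number randomised.** The précis says "In each cohort, twenty individuals will be randomized with 10 each in the mindful self-compassion group", which over four cohorts gives 40 per arm; section 3 agrees. Section 4.3.4 instead begins "In all but the first two cohorts, as soon as 14-20 eligible adolescents qualify for enrollment", which leaves two cohorts, or at most 20 per arm. Section 6.2.2 exempts the first two groups, one of each program. If those two groups make up one cohort, three cohorts of 10 per arm remain, or 30 per arm.

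**4. Precision of the difference.** Half-width = 1.96 × √(2p(1−p)/n), in percentage points:

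| Drop-out p in each arm | n = 40 | n = 30 | n = 20 |
|---|---|---|---|
| 10% | 13.1 | 15.2 | 18.6 |
| 25% | 19.0 | 21.9 | 26.8 |
| 40% | 21.5 | 24.8 | 30.4 |

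For example, at p = 25% and n = 40: 1.96 × √(2 × 0.25 × 0.75/40) = 1.96 × 0.0968 = 0.190.

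**5. Power, if the rates were tested.** Pooled z-test, with Fisher's exact test in brackets:

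| Drop-out | 40 per arm | 20 per arm |
|---|---|---|
| 20% v 30% | 0.18 (0.12) | 0.11 (0.06) |
| 20% v 40% | 0.50 (0.41) | 0.28 (0.19) |
| 20% v 50% | 0.82 (0.75) | 0.51 (0.41) |

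Against 20%, power of 80% by the z-test needs about 50% drop-out in the other arm at 40 per arm, and about 62.5% at 20 per arm.

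**6. The pooled alternative.** In the example of step 2, 20 of 80 leave. The pooled proportion is 25%, with half-width 1.96 × √(0.25 × 0.75/80) = 9.5 points. With 40 randomised and the same proportion it is 1.96 × √(0.25 × 0.75/40) = 13.4 points. This estimate responds to the level of loss and is about twice as precise as the difference between arms (19.0 points at 40 per arm).

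**The case against.** The defence has real force on four points.

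First, a reader might infer that the plan would declare randomisation accepted whatever the loss. The documents do not support that. Section 9.6.2 sets no decision rule, section 9.1 says statistical hypotheses are not relevant to this grant, and anyone comparing two rates sees both of them. Rates of 25% and 25% would be visible as heavy loss.

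Second, a reader might infer that such loss would pass unnoticed. It would not. Losing 10 of 40 in each arm caps completion at 60/80 = 75%, below the 80% criterion in section 9.6.2 item 3 and in section 8 of the monitoring plan. Item 4b has non-completers interviewed by telephone about why they left. However, neither element is linked to acceptance of randomisation, and neither reaches families who decline before enrolment.

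Third, the comparison is not empty. Leaving the less wanted arm on learning the assignment is one form of not accepting allocation, and drop-out by arm can respond to it. That signal cannot be separated from the content, timing or place of the class, and by step 5 it must be large to be seen.

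Fourth, the précis speaks of the feasibility of randomising and does not list acceptance of chance allocation among its components. The mismatch therefore rests on section 9.2.1, which does state that purpose.

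Wide intervals are normal in a pilot and are not in themselves a fault.

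**Conclusion.** The concern holds in a limited form. The one measure named for acceptability of randomisation cannot reflect refusal, its contrast does not respond to loss shared by both arms, and any difference is confounded with program appeal. If the restriction in section 9.5 is applied to it, families who leave on learning their assignment drop out of the count as well. The documents do not say whether that restriction covers the feasibility analyses, so this last part is conditional.

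The effect of refusal and of common loss follows from the text and needs no assumed rate. The half-widths and power figures rest on assumed drop-out, a 5% level and 20 to 40 per arm. The wider conclusion that the study learns nothing about overall retention is not supported. What is missing is a measure tied to randomisation itself, and this should be corrected.

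**What to change.** Replace the sentence in section 9.6.2 with two measures of acceptance of randomisation:

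- **(a)** Among all randomised participants, pooled over arms, the proportion who leave between disclosure of assignment and class 1, with a 95% interval. State that the at-least-one-class restriction in section 9.5 does not apply to it. The allocation and attendance records already planned should supply this.
- **(b)** Among otherwise eligible families, the proportion who decline because of randomisation, with a 95% interval. Consent precedes the psychologist's assessment (section 4.3.2), so eligibility here means as far as screening had gone. Code the reason from the screening log where one was recorded, and add a reason field prospectively if recruitment is still open. Sections 5.1.3 and 9.5.1 describe data collection in the past tense, so it may not be; in that case state the gap as a limitation.

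Report both measures only for cohorts that were actually randomised, after reconciling sections 4.3.4 and 6.2.2 with the précis and section 3. Keep drop-out by arm, relabelled as comparative acceptability of the two programs.

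The cost is protocol wording and at most one log field, with no added visits or staff. The downside is small: some families will give no reason, and reasons may be missing for cohorts already recruited.
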